6.5 Discharge Assessments

- Physical examination/Vital signs
- Adverse event
- COVID-19 Assessment: If the patient has a COVID-19 test at any point after enrollment in the study, details of the test, date conducted, and outcome should be captured in the COVID-19 Assessment Log Form.
- Concomitant use of anticoagulant and antiplatelet medications

For physical examination and vital signs, refer to **Section 6.8** for further details.

6.6 90-day Follow-up Assessments

All subjects are required to have an office visit for the 90-day (± 30 days) clinical follow-up as well as echocardiographic follow-up. If a subject remains hospitalized 90 days post-

device removal, a 90-day follow-up form is still required. To aid in follow-up compliance, if necessary, an independent service (e.g. Hawthorne Effect) may be utilized to provide in-home visits for both the clinical and echocardiographic follow-up.

- Physical examination
- NYHA heart failure class
- Quality of life questionnaires (SAQ and EQ-5D-5L)
- Echocardiogram (performed per the Echocardiographic Core Laboratory Guidance with images uploaded to the Echocardiographic Core Laboratory via Bioclinica website)
- Adverse event
- COVID-19 Assessment: If the patient has a COVID-19 test at any point after enrollment in the study, details of the test, date conducted, and outcome should be captured in the COVID-19 Assessment Log Form.
- Concomitant use of anticoagulant and antiplatelet medications

For physical examination and echocardiogram, refer to **Section 6.8** for further details.

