7.3 Adverse Event and Device Deficiency Reporting

7.3.1 Adverse Event Reporting

Safety surveillance and reporting starts as soon as the subject is registered in the clinical investigation. Safety surveillance and reporting will continue until the last follow-up visit has been performed, the subject is deceased, the subject concludes participation in the clinical investigation or the subject withdraws from the clinical investigation. All adverse event data, including deaths and device deficiencies, will be collected throughout the time period defined above and will be reported to the Sponsor on a CRF. Additional information with regard to an adverse event should be updated within the appropriate CRF.

Unchanged, chronic, non-worsening or pre-existing conditions are not AEs and should not be reported.

An offline form will be made available to allow the investigator to report SAEs in the event the entry cannot be made in the EDC. This does not replace the EDC reporting system. All information must still be entered in the EDC system as soon as feasible.

Non-cardiac related abnormal laboratory values will not be considered AEs unless:

1. The investigator determined that the value is clinically significant,
2. The abnormal lab value required intervention, or
3. The abnormal lab value required subject withdrawal from the clinical investigation.

In this clinical investigation, all adverse events, regardless of their relationship to the devices, are to be documented on the appropriate CRF throughout the 90-day follow-up visit. Anticipated adverse event definitions can be found in **Appendix II**.

SAE Reporting

The investigator should report all SAEs to the Sponsor as soon as possible but no later than the timelines outlined below.

Clinical Site	Reporting timelines
All Sites	SAEs must be reported to the Sponsor no later than 3 calendar days from the day the site personnel became aware of the event or as per the investigative site's local requirements, if the requirement is more stringent than those outlined above.

The date the site staff became aware the event met the criteria of an SAE must be recorded in the source document. The Investigator will further report the SAE to the local IRB according to the institution's IRB reporting requirements.

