2.2.2 Descriptive Statistics for Categorical Variables

For binary variables (e.g. gender, diabetic status, etc.), results within treatment arm will be summarized with subject counts and percentages/rates, and where applicable, with exact 95% Clopper-Pearson¹ confidence intervals.

For events of interest, relative risks (i.e., the ratio of rates), confidence interval for the relative risks, the difference in rates and the confidence interval for difference in rates, and p-values may also be presented for hypothesis generating purposes.

For the determination of event rates, the denominators are defined as below based on the type of events.

- Primary endpoint event and its components

The denominator of the primary endpoint event rate will exclude subjects in the analysis population who terminated from the study [REDACTED] without a primary endpoint event or any subject who completes the 90-day follow-up without aortic insufficiency data at either baseline or 90-day follow-up and without a primary endpoint event. The same denominator rule will apply to individual component of the primary endpoint except for change in aortic insufficiency, which is an imaging endpoint and will follow the denominator rule set forth for missing data handling.

Statistical Analysis Plan

- Site-reported Adverse Events, Adverse Device Effects and Adverse Event related Descriptive Endpoints

[REDACTED]

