2.2.3 Survival Analyses

Survival analysis will be conducted to analyze time-to-event variables. Subjects without events will be censored at their last known event-free time point. Subjects who withdrew from the study will be censored at the date of withdrawal. Survival curves will be constructed using Kaplan-Meier⁴ estimates. Summary tables for endpoints will include event (failure) rates, Greenwood standard error and confidence interval for the event rates.

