2.9 Handling of Missing Data

All analyses will be based on available data with missing data excluded.

[REDACTED]

[REDACTED]

Statistical Analysis Plan

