2.12 Sensitivity Analysis

The following sensitivity analyses of the primary endpoint will be carried out:

Worst Case Scenario Analysis

Tipping Point Analysis

Statistical Analysis Plan

Multiple Imputation

3.0 **DESCRIPTIVE ENDPOINTS AND ADDITIONAL DATA**

Data in the feasibility phase of the clinical investigation will be analyzed separately from data in the pivotal phase of the clinical investigation. Data collected for both roll-in and randomized subjects will be summarized descriptively. The results of the roll-in cohort will be analyzed as adjunctive data, separate from the results of the randomized cohort.

3.1 **Baseline and Demographic Characteristics**

The following baseline and demographic variables will be summarized: gender, age, height, weight, baseline risk factors, medical history, morphology, quantitative coronary angiography, echocardiogram, implant procedural characteristics, device usage, and quality of life, etc.

3.2 **Adverse Events**

The start of the index procedure will be a reference start time for summarizing all adverse events. All of the adverse device effects, serious adverse device effects, UADEs will be summarized for all subjects who registered in this trial in terms the number of events and the percentage of subjects with events.

All CEC adjudicated adverse events will also be summarized for all subjects who registered in the trial by treatment arms in terms the number of events and the percentage of subjects with events.

Statistical Analysis Plan

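### SAP 2.2.2 drops event-free completers who lack aortic-insufficiency data from the denominators of six components that need no such data

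*SAP*

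**What the plan says.** The primary endpoint (SAP 1.4.1, Protocol 4.1) has seven components. Six are clinical: cardiovascular death, MI, stroke, unplanned repeat revascularization, BARC 3 or 5 bleeding to 14 days after device removal, and severe hypotension on device support. The seventh is change in aortic insufficiency (AI) on echocardiography.

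SAP 2.2.2 takes two groups out of the composite's denominator. The first is subjects who left the study without a primary endpoint event (the timing is redacted). The second is "any subject who completes the 90-day follow-up without aortic insufficiency data at either baseline or 90-day follow-up and without a primary endpoint event". It then says "The same denominator rule will apply to individual component of the primary endpoint except for change in aortic insufficiency". AI change is set apart as an imaging endpoint and sent to the missing-data rule.

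The visible part of that rule, in SAP 2.9 and Protocol 8.8, reads "All analyses will be based on available data with missing data excluded"; the rest of 2.9 is redacted. On data capture, Protocol 7.3.1 states that "all adverse events, regardless of their relationship to the devices, are to be documented on the appropriate CRF throughout the 90-day follow-up visit". For events of interest, SAP 2.2.2 also allows relative risks and rate differences with confidence intervals, and "p-values may also be presented for hypothesis generating purposes".

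**The concern.** Excluding an AI-missing, event-free completer from the composite makes sense, because that subject might have had an unrecorded AI event. The reason disappears for stroke or bleeding. A missing echocardiographic reading says nothing about whether those events happened, and a subject who came to the 90-day visit has been followed for them. Carrying the exclusion over discards known non-events and keeps every event.

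The component tables show a reader what drives the composite, which mixes safety and effectiveness in a trial meant to support pre-market approval. If the exclusion applies, all six clinical rates are inflated together. If AI data are missing more often in one arm, the relative risks and rate differences for all six shift in the same direction, for a reason unrelated to the devices' effect on those outcomes.

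**Working it through.** **Do the six components need an AI reading?** By their definitions in SAP 1.4.1, no. For bleeding and severe hypotension the observation window closes well before the 90-day echocardiogram.

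**Is the excluded subject's status known?** Yes. The rule concerns subjects who complete the 90-day follow-up, and Protocol 7.3.1 has all adverse events recorded through that visit.

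**Direction.** A subject with a given component event also has a primary endpoint event, so that subject is never excluded. Numerators stay fixed and denominators shrink.

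**Inputs.**
- From SAP 2.4: composite rate p = 20% (stated for Impella only; assumed here for both arms), and N = 473, that is 315 HeartMate PHP plus 158 Impella. The 2:1 split checks: 473 × 2/3 = 315.3 and 473/3 = 157.7.
- Assumed, not in the documents: m, the share of subjects open to exclusion who complete without AI data, from 1% to 20% and unrelated to events; a true stroke rate c of 3.0%; early terminators ignored.

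The plan gives no figure of its own for AI missingness or for the component rates, so there is none to reproduce.

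**Two readings of the same rule.** If primary endpoint event keeps its composite meaning, the share retained is 1 − m(1 − p). If it is taken to mean the component in question, the share retained is 1 − m(1 − c). In each case the reported rate is the true rate divided by the share retained.

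| m | Composite reading: factor | Removed of 473 | 3.0% reported as | Component reading (stroke): factor | Removed of 473 | 3.0% reported as |
|---|---|---|---|---|---|---|
| 1% | 1.008 | 3.8 | 3.02% | 1.010 | 4.6 | 3.03% |
| 5% | 1.042 | 18.9 | 3.13% | 1.051 | 22.9 | 3.15% |
| 10% | 1.087 | 37.8 | 3.26% | 1.107 | 45.9 | 3.32% |
| 15% | 1.136 | 56.8 | 3.41% | 1.170 | 68.8 | 3.51% |
| 20% | 1.190 | 75.7 | 3.57% | 1.241 | 91.8 | 3.72% |

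Example at m = 10%, composite reading: 1 − 0.10 × 0.80 = 0.92, and 1/0.92 = 1.087. The result is not sensitive to p: at m = 20%, the factor is 1.205 for p = 15% and 1.176 for p = 25%.

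**If both readings must be missing.** Let b be the share of baseline readings missing, 1% to 5%, independent of 5% to 20% missing at 90 days. The share retained is 1 − b × m × (1 − p). The factor runs from 1.0004 to 1.0081, with 0.2 to 3.8 of 473 removed.

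**Unequal missingness, equal true rates.** Take 5% missing on HeartMate PHP and 15% on Impella.
- Composite reading: shares retained are 1 − 0.05 × 0.80 = 0.96 and 1 − 0.15 × 0.80 = 0.88. The relative risk is 0.88/0.96 = 0.917, or 0.96/0.88 = 1.091 if the arms are swapped. Removed: 0.04 × 315 = 12.6 and 0.12 × 158 = 19.0.
- Component reading, stroke: 0.8545/0.9515 = 0.898, or 1.114 swapped.

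**Against sampling error.** With 9 events in 315 subjects, the 95% Clopper-Pearson interval is 1.3% to 5.4%. For a rare component the bias is smaller than this, but it is systematic and acts on all six.

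**The case against.** The strongest reply concerns wording. To be without data at either of two visits can be read as lacking both, and then almost nobody is excluded. Baseline echocardiography is also part of eligibility, so missing both should be rare. This stands as a real ambiguity. Since a change measure needs both readings, lacking one is the likelier intent, but that is an inference and the SAP should settle it.

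A second reply is that the net direction under the full rule is not established. On the composite reading, someone with an early bleed who later withdraws stays in the stroke denominator as event-free, which pulls that rate down. Likewise, a subject who leaves event-free after day 14 has known bleeding and hypotension status but may still be excluded. Both points are fair. They arise from the early-termination clause, whose timing is redacted, and they do not justify the AI exclusion. The upward bias claimed here is that of the AI clause alone.

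Third, a shared denominator lets the components be set beside the composite in the same subjects. The SAP has already given that up by treating AI change separately.

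Fourth, there are offsets. SAP 3.2 says "All CEC adjudicated adverse events will also be summarized for all subjects who registered in the trial by treatment arms". Kaplan-Meier summaries in SAP 2.2.3 use the rule "Subjects without events will be censored at their last known event-free time point", although that section does not name the components. Protocol 6.6 provides an independent service that "may be utilized to provide in-home visits for both the clinical and echocardiographic follow-up", which should keep missing readings down. These limit the harm, but the same event type could then be reported with two denominators. Redacted text in 2.2.2 or 2.9 could also qualify the rule, although the visible sentence is explicit and sends only AI change elsewhere.

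**Conclusion.** The concern holds. Followed as written, the rule gives wrong denominators for six clinical components, and it departs from the SAP's own visible principle of using available data. On the likelier reading, where one missing AI value is enough, the rates are multiplied by 1.04 at 5% missing and 1.19 at 20%. Unequal missingness of 5% and 15% moves a true relative risk of 1 to 0.92 or 1.09. These figures rest on assumed missingness unrelated to events, a 20% composite rate in both arms, and no early terminators. If few AI readings are missing, or if only subjects missing both are meant, the effect is near zero.

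The consequence is confined to descriptive, hypothesis-generating tables. This sentence does not alter the primary non-inferiority test. It is worth correcting before the data are unblinded, but it does not threaten the trial's main conclusion.

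**What to change.** Replace the sentence that extends the rule to the components with text such as:

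> For each component other than change in aortic insufficiency, the early-termination exclusion applies as stated for the composite, but the exclusion for missing aortic insufficiency data does not. Every subject who completes the 90-day (± 30 days) clinical follow-up, or who had that component event, is counted whatever the echocardiogram status. Aortic insufficiency data are missing if the baseline reading or the 90-day reading is missing.

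The AI-data condition then applies only to the composite and to AI change. The wording leaves the partly redacted early-termination rule untouched, and it keeps event-free subjects whose valid visit falls on days 60 to 89.

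The cost is this short SAP edit and minor table programming, with no new data. Component and composite tables will carry different Ns, which a footnote should explain.

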2.2.3 Survival Analyses

Survival analysis will be conducted to analyze time-to-event variables. Subjects without events will be censored at their last known event-free time point. Subjects who withdrew from the study will be censored at the date of withdrawal. Survival curves will be constructed using Kaplan-Meier⁴ estimates. Summary tables for endpoints will include event (failure) rates, Greenwood standard error and confidence interval for the event rates.

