2.3 Endpoint Analysis

2.3.1 Primary Endpoint(s)

The primary endpoint, a composite of safety and effectiveness at 90 days, will be evaluated using the difference in event rates in the ITT population of the pivotal phase. The hypothesis test is designed to show non-inferiority of HeartMate PHP to Impella for the primary endpoint with one-sided alpha of 0.025.

[REDACTED]

ICER

[REDACTED]

If non-inferiority is met, superiority testing will be performed with a two-sided alpha of 0.05.

[REDACTED]

[REDACTED]

The data will be analyzed for superiority using Fisher's exact test.

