3.3 Subject Early Termination

Subject early termination reasons including deaths, withdrawals, lost-to-follow-up, etc. will be summarized by treatment arms at the 90-day follow-up visit.

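### The Kaplan-Meier failure rates in SAP 2.2.3 have no rule for competing deaths, so for endpoints that do not count all deaths they slightly overstate the 90-day cumulative incidence

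*SAP*

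**What the plan says.** SAP 2.2.3 is a short general paragraph on time-to-event methods. Its scope is "Survival analysis will be conducted to analyze time-to-event variables", and the visible text does not list those variables. It gives two censoring rules. The first is "Subjects without events will be censored at their last known event-free time point". The second is "Subjects who withdrew from the study will be censored at the date of withdrawal". On the estimator it says "Survival curves will be constructed using Kaplan-Meier". On reporting it says "Summary tables for endpoints will include event (failure) rates, Greenwood standard error and confidence interval for the event rates". It does not mention death or competing events, and no cumulative incidence estimator appears elsewhere in the visible text.

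The plan expects deaths. SAP 3.3 will tabulate "Subject early termination reasons including deaths" along with withdrawals and losses to follow-up.

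The main analysis uses a different measure. Under SAP 2.3.1 the composite "will be evaluated using the difference in event rates in the ITT population of the pivotal phase", with Fisher's exact test for superiority. SAP 2.2.2 sets a denominator for the composite proportion and adds "The same denominator rule will apply to individual component of the primary endpoint except for change in aortic insufficiency".

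**The concern.** A subject who dies stroke-free is a subject without a stroke, so the general rule censors that subject at or before death. Kaplan-Meier assumes that censored subjects remain exposed to the same later risk as those still under observation. A dead subject does not. One minus Kaplan-Meier then describes a hypothetical population in which nobody dies of anything outside the endpoint. It does not give the proportion of subjects who have the event by 90 days, and its Greenwood interval is an interval for the hypothetical quantity.

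Two things are at stake. A reader will take the tabulated failure rate as a patient's 90-day risk, and it will be somewhat too high. In addition, if the arms have the same true event proportion but different numbers of prior deaths, the Kaplan-Meier rates will differ for that reason alone.

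**Working it through.** The plan gives no Kaplan-Meier rate, component rate or death rate, so there is no figure of its own to reproduce here. The sample size of 473 does not depend on this rule. Its split is used only for scale.

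**Inputs**
- From SAP 2.4: 315 HeartMate PHP and 158 Impella subjects (315 + 158 = 473).
- Assumed, because the documents give no values: E, the true 90-day cumulative incidence of the event, 5% or 10%; D, the 90-day cumulative incidence of death without the event, 2%, 3% or 5%.

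**Step 1: constant hazards.** The total cumulative hazard is H = -ln(1 - E - D). The event's share is h = H × E/(E + D). With deaths censored, Kaplan-Meier estimates 1 - exp(-h).

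Example with E = 10%, D = 5%: H = -ln(0.85) = 0.1625; h = 0.1625 × 10/15 = 0.1083; 1 - exp(-0.1083) = 10.268%.

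**Step 2: bounds for other timing.** If every death precedes every event, all events fall on the surviving fraction and Kaplan-Meier gives E/(1 - D). This is the largest value possible. If every event precedes every death, there is no excess.

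| E | D | 1 - KM, constant hazards | Excess (points) | Maximum E/(1 - D) | Maximum excess (points) |
|---|---|---|---|---|---|
| 5% | 2% | 5.052% | 0.052 | 5.102% | 0.102 |
| 5% | 3% | 5.078% | 0.078 | 5.155% | 0.155 |
| 5% | 5% | 5.132% | 0.132 | 5.263% | 0.263 |
| 10% | 2% | 10.105% | 0.105 | 10.204% | 0.204 |
| 10% | 3% | 10.159% | 0.159 | 10.309% | 0.309 |
| 10% | 5% | 10.268% | 0.268 | 10.526% | 0.526 |

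The relative excess cannot be more than 1/(1 - D) - 1, which is 2.0% at D = 2% and 5.3% at D = 5%.

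**Step 3: false arm difference.** Take the same true E = 10% in both arms, with deaths of 5% and 3%. Under constant hazards the difference is 10.268 - 10.159 = 0.109 points. At the bound it is 10.526 - 10.309 = 0.217 points.

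**Step 4: scale.** The standard error of the arm difference at 10% is sqrt[0.10 × 0.90 × (1/315 + 1/158)] = 0.0292, or 2.92 points. The false difference is 0.109/2.92, about 4% of one standard error.

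**Step 5: the same subject under the two SAP rules.** Cardiovascular death is itself a primary endpoint event. A subject who dies of a cardiovascular cause without a stroke therefore stays in the SAP 2.2.2 stroke denominator and counts as having no stroke. Under SAP 2.2.3 that subject is censored. If both displays are produced for stroke, they can differ for this reason alone.

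**The case against.** The strongest reply is that SAP 2.2.3 never says deaths are censored. That is read from a general sentence and from silence about death. The time-to-event variables are not named, and the descriptive-endpoint sections are largely blacked out, so a list or a rule for deaths may be there. This stands as a limit on what can be said: it cannot be shown which endpoints get Kaplan-Meier rates. It does not remove the point, because the visible wording, applied as written, censors a subject who dies event-free.

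A reader might infer that the trial's 90-day component rates, or the primary result, are inflated. The documents do not support that. SAP 2.2.2 and 2.3.1 define the composite and component rates as proportions and test the composite on them. No visible hypothesis test uses Kaplan-Meier.

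A reader might also infer that every component is affected alike. It is not so:
- Severe hypotension is counted only on device support, and Protocol 2.2.2 describes the device as temporary, under 6 hours, so death hardly competes.
- Bleeding is counted only to 14 days after device removal.
- For cardiovascular death, only non-cardiovascular death competes.
- Change in aortic insufficiency is treated in SAP 2.2.2 as an imaging endpoint, not obviously a time-to-event variable.

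Larger effects can be produced with more deaths. At E = 10%, deaths of 12% against 4% give 10.68% and 10.21%, about 0.5 points apart. Nothing in the documents supports a 12% death rate. If those deaths were mainly cardiovascular, 10% plus 12% would exceed the 20% assumed for the whole composite on Impella. An 8-point gap in deaths would in any case dominate the interpretation.

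Finally, the false arm difference assumes equal true event proportions. If the event hazards while alive were equal instead, the Kaplan-Meier rates would agree and the cumulative incidences would differ. Kaplan-Meier is a fair summary of that hazard, but the SAP labels its output event rates, which readers will take as proportions.

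**Conclusion.** The concern holds for supplementary displays only. As written, SAP 2.2.3 gives Kaplan-Meier failure rates that overstate the 90-day cumulative incidence of any endpoint that does not count all deaths. The excess is about 0.05-0.3 points under constant hazards for events of 5-10% and prior deaths of 2-5%. It is at most 0.53 points if all deaths come first, and close to zero if events cluster at the procedure. Deaths of 5% against 3% add about 0.1 points of false arm difference at a 10% event rate, far inside the sampling error.

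This rests on assumed event and death rates, on the literal reading of the censoring sentence, and on no rule for deaths in the withheld text. The non-inferiority test, the superiority test and the SAP 2.2.2 proportions do not change. This is a cheap improvement, not a threat to the trial's conclusion.

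**What to change.** In SAP 2.2.3, state that for every time-to-event endpoint that does not include all-cause death, the 90-day rate will be the Aalen-Johansen cumulative incidence with its own standard error and confidence interval, with death outside the endpoint as the competing event. For cardiovascular death, the competing event is non-cardiovascular death. Keep Kaplan-Meier with Greenwood errors for all-cause death and for endpoints that include it. If the withheld text does not already list the time-to-event variables, list them here.

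The cost is about one SAP sentence and a different standard estimator. Deaths are already reported under Protocol 7.3.1. Sample size, alpha and primary analysis stay the same.

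There are two downsides. The rates will be slightly lower and less comparable with reports that used Kaplan-Meier. They will also still not match the SAP 2.2.2 proportions exactly. Those denominators drop some subjects who terminated without a primary event (part of that rule is blacked out) and event-free completers who lack aortic insufficiency data. Because SAP 3.3 counts deaths as early terminations, event-free non-cardiovascular deaths may be among those dropped. A footnote on each table naming the estimator and denominator would prevent confusion.
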